# 4.3 Handling of Dropouts or Missing Data

Subject-level listings will present data as reported. Missing or partially missing dates that are required for date-dependent definitions (e.g., treatment-emergent adverse events, concomitant medications) will be assumed to be the most conservative date possible.

An adverse event (AE) with a completely missing start date will be considered treatment-emergent; similarly, an AE that started the same month and year as IP administration but with a missing start day will be considered treatment-emergent.

AEs with missing seriousness will be counted as "serious" in tables and missing in listings; likewise, AEs with missing severity will be counted as "severe" in tables and missing in listings, and AEs with missing relatedness to the IP and/or IP administration procedure will be counted as "possible" and missing in listings.

Medical history events with missing stop dates will be considered ongoing. Medications with missing stop dates will be considered in concurrent use during the study and counted in the summary table of concomitant medications unless the start date is after the last IP administration.

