#### 13.2.4. Reporting Adverse Events

All adverse events are collected from the time of signing informed consent for trial participation until completion of 6 months or early termination, whichever occurs first. All AEs occurring after the initiation of the IV catheter placement for the initial dose of CAP-1002 will be considered treatment emergent. Any ongoing adverse event that has not been resolved at the time of trial completion or early termination for a subject will be marked as ongoing on the adverse event case report form (CRF).

All AEs will be entered into the electronic data capture (EDC) system by trained site personnel at the investigative site.

Expected and unexpected SAEs must be reported to Capricor and entered into the EDC system within 24 hours of discovery of the event. For events that do not have complete information available at the time of initial report, the investigative site will submit all available information at the time of the submission. All SAE Report Forms must be signed by an Investigator and submitted with available source documentation. All source documentation must be de-identified prior to submission.

ALL SAES and subsequent follow-up information must be reported to Capricor, or designee, via email or fax as outlined in the Manual of Procedures and Safety Plan.

All SAEs must be reported to the respective IRB in accordance with the investigative site's policies. Copies of the submission will be collected by Capricor.

All SAEs will be reported to the DSMB at least semi-annually, or more frequently at the discretion of the Medical Monitor.

Capricor will promptly upon discovery, report serious and unexpected adverse events for which there is a reasonable possibility that the investigative therapy (i.e. administration product and/or investigative product) caused the events, to the Food and Drug Administration (FDA) in accordance with 21 CFR 312.32 regulations and ICG E2A guidelines.

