# 7.1 Adverse Events

Adverse events will be coded using the Medical Dictionary for Regulatory Activities (MedDRA) coding system (Version 21.0). Potential primary safety endpoints, described in Section 2.2.1, will be adjudicated by an independent Clinical Events Committee (CEC).

The following AEs are defined as treatment-emergent AEs (TEAEs):

- AEs occurring after the initiation of the IV catheter placement for the initial dose of IP; or
- AEs with a completely missing start date, or similarly, AEs that started the same month and year as IP administration but with missing start day.

Subject listings of all adverse events as reported will be provided. A separate listing will be done for TEAEs as adjudicated by the CEC. All summary tables will be reported using as adjudicated by the CEC.

An overall summary table will be presented by treatment group that summarizes subject with the following:

- Any TEAEs
- TEAEs by maximum severity
- TEAEs and serious TEAEs by greatest degree of relationship to IP or IP administration
- TEAEs and serious TEAEs by greatest degree of relationship to IP only
- TEAEs and serious TEAEs by greatest degree of relationship to IP administration only
- Serious TEAEs
- TEAEs leading to study discontinuation, and
- TEAEs leading to death

In addition, TEAEs will be summarized overall by system organ class and preferred term and by severity and by relationship to the IP and IP administration procedure.

Deaths, AEs that resulted in study discontinuation, serious adverse events (SAEs), serious TEAEs and AEs within 24 hours of IP administration will be listed and summarized.

Summaries of 'related' TEAEs, will include TEAEs with a reported relationship to IP and/or IP administration of "Probable" or "Possible". Adverse events will be displayed by MedDRA System Organ Class and Preferred Terms, with subjects who have the same adverse event counted only once for that event and with subjects who have more than one adverse event within a System Organ Class counted only once in that System Organ Class. The numbers and percentages of subjects reporting an event as well as the number of events that were reported will be displayed.

Frequency tables will be ordered by decreasing percentage in the SOCs, then alphabetically. Within each SOC, PTs will be ordered by decreasing percentage then alphabetically.

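### The SAP's missing-start-date rule ignores the stop date, so an AE recorded as over before the first infusion procedure is counted as treatment-emergent

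*SAP*

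**What the plan says.** Protocol 13.2.4 sets the boundary: "All AEs occurring after the initiation of the IV catheter placement for the initial dose of CAP-1002 will be considered treatment emergent". The same section opens the collection window earlier: "All adverse events are collected from the time of signing informed consent for trial participation until completion of 6 months or early termination". The schedule of assessments (Protocol Table 3, SAP Appendix B) places screening up to 30 days before Day 1 and records AEs at that visit.

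SAP 4.3 begins with a general principle: missing or partial dates needed for date-dependent definitions "will be assumed to be the most conservative date possible". It then gives two specific AE rules. The first is "An adverse event (AE) with a completely missing start date will be considered treatment-emergent". The second is that "an AE that started the same month and year as IP administration but with a missing start day will be considered treatment-emergent".

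SAP 7.1 repeats them as the second of two alternatives that define a TEAE: "AEs with a completely missing start date, or similarly, AEs that started the same month and year as IP administration but with missing start day". The first alternative is the protocol's catheter-placement boundary.

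Neither SAP section attaches a condition on the stop date to these rules.

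**The concern.** A conservative missing-data rule should settle what the data leave open. If the start date is unknown and nothing else is recorded, calling the event treatment-emergent is reasonable. If the stop date is recorded and falls before the first infusion procedure, the data already show that the event was not treatment-emergent. The rule nevertheless classes it as one.

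The tables affected are the TEAE summaries and, in a narrower set of cases, the primary safety endpoint of TEAEs related to IP or its administration. SAP 4.3 also counts missing seriousness as serious, missing severity as severe and missing relatedness as possible. A poorly documented event from the screening period could therefore appear in the serious or related TEAE rows although it ended before exposure. With at most 10 subjects, a single event can be visible in a percentage.

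**Working it through.** The plan gives no figure to reproduce on this point: there is no power calculation and there are no formal hypotheses (Protocol 14.1). The check is of the rule's logic, followed by the arithmetic of one affected subject.

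**Inputs**

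- Emergence boundary and collection from consent: Protocol 13.2.4.
- Missing-date rules: SAP 4.3 and 7.1.
- Screening up to 30 days before Day 1: Protocol Table 3. Infusion normally within 14 days of confirmed eligibility: Protocol 7.1.
- AE end dates are expected in the data: SAP 4.2 uses them to calculate event duration.
- Up to 10 subjects, single arm: Protocol 7.3.
- Subjects counted once per preferred term and once per system organ class: SAP 7.1.

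**Step 1. Apply the rule to test events.** Day 1 is set to 20 March 2019 for illustration.

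| Start | Stop | Rule as written | With a stop-date exception |
|---|---|---|---|
| missing | 10 March | TEAE | not TEAE |
| March 2019, day missing | 10 March | TEAE | not TEAE |
| 5 March | 10 March | not TEAE | not TEAE |
| missing | missing | TEAE | TEAE |
| March 2019, day missing | 25 March | TEAE | TEAE |

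The second and third rows could be the same event, differing only in whether the start day was entered. The stop date shows in both that it ended before Day 1, yet the rule gives opposite answers. The last two rows show that an exception leaves undetermined events treatment-emergent.

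**Step 2. How often a pre-infusion onset falls in the infusion month.** This matters for the missing-day rule. Assume Day 1 is equally likely on any date in 2019. For Day 1 on day d of a month and a window of W days, the share of pre-infusion days in the same month is min(d − 1, W)/W.

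- W = 30: mean day of the month = (7 × 496 + 4 × 465 + 406)/365 = 5738/365 = 15.72; share = (15.72 − 1)/30 = 0.49.
- W = 14: mean of min(d − 1, 14) = (7 × 329 + 4 × 315 + 287)/365 = 3850/365 = 10.55; share = 10.55/14 = 0.75.

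Roughly half to three quarters of pre-infusion days would fall within reach of that rule. It acts only if the start day is missing, and the documents do not say how often that happens.

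**Step 3. Size of one affected subject.** If the subject has no other qualifying event in the row, the row moves from 0/n to 1/n.

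- n = 10: 1/10 = 10 percentage points. The exact 95% interval is 0.3% to 44.5% for 1/10 and 0% to 30.8% for 0/10. These intervals are for illustration; SAP 7.1 plans counts and percentages.
- n = 8 (assumed): 1/8 = 12.5 points.
- n = 5 (assumed): 1/5 = 20 points.

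If the subject already has a genuine TEAE in that row, the subject percentage changes by 0. Only the event count rises, by one.

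**Step 4. Compare with the SAP's handling of medications.** SAP 5.10 classes a medication stopped before the start of the IP administration procedure as pre-treatment. In SAP 4.3, the rule for a missing medication stop date has an exception based on the known start date. The AE rules have no counterpart.

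**The case against.** The best defence is the opening principle of SAP 4.3. A start date later than a recorded stop date is not a possible date, so the AE rules might be read as already limited by the stop date. Part of this stands: the SAP nowhere says that a known stop date is to be ignored, and a reader who infers such an instruction goes beyond the text. But the AE sentences do not impute a date that the stop date could limit. They assign treatment-emergent status directly, and SAP 7.1 restates them as a definition without the general principle. A programmer working from 7.1 would flag the event.

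A second defence is CEC adjudication. All potential primary safety endpoints go to the CEC, and SAP 7.1 bases its summary tables on adjudicated events. SAP 7.1.1 lets the committee combine events, rename them or reclassify them as non-AEs. It does not describe correcting emergence by date, and an event that ended before treatment is still an AE. Adjudication is therefore a safeguard for the primary endpoint but not a described remedy.

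Third, the trigger is narrow, and this stands. It needs an onset after consent, a missing start date or day, and a recorded stop before the infusion procedure, in a trial of at most 10 subjects. Data queries and monitoring (Protocol 16.1, 16.2) should resolve many missing dates. Clinically significant examination findings before treatment go to medical history (Protocol 13.1.3).

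Fourth, the direction is conservative, no significance conclusions are planned, and listings show dates as reported. That also stands and limits the weight of the point.

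**Conclusion.** The point holds as a minor correction. In the cases described, the stated rule gives a classification that contradicts both the recorded data and the protocol's definition.

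Two stronger readings are not supported. A reader might infer that every affected event adds at least 10 percentage points. It does so only when the subject has no other qualifying event in that row, because subjects are counted once. A reader might also infer that the related-TEAE endpoint is generally inflated. That needs a further condition: relatedness must be missing, and so counted as possible, or already assessed as probable or possible. Protocol 13.2.3 requires the Investigator to evaluate causality for every AE. The criteria in Protocol 13.2.2 mostly call for a temporal link to exposure, although one route to possible does not.

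The conclusion assumes that the rules are programmed as written and that the recorded stop date is correct. The frequency is unknown and probably low. The error can only overstate TEAEs.

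**What to change.** Add the same exception to the AE rules in SAP 4.3 and to the second alternative of the TEAE definition in SAP 7.1:

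> unless the recorded stop date, or the known part of a partial stop date, shows that the event ended before IV catheter placement for the first dose of IP was initiated.

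The cut-off should be catheter placement, not the start of the infusion, because that is the TEAE boundary in Protocol 13.2.4 and SAP 7.1. Access-site pain or bleeding, which Protocol 13.2.1.3 lists among the procedure risks, could begin at catheter placement and resolve before the infusion starts. An infusion-based cut-off would wrongly remove such an event if its start date were missing.

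The exception should rest on the stop date, since a partial start date cannot show that an event has ended. An event with no stop date, or with a stop date that does not settle the order (for example Day 1 with no time recorded), stays treatment-emergent.

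The cost is one clause in two places and a small programming change. It needs no new data and no change to trial conduct.

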#### Table 3: Schedule of Assessments

Procedure / Event 	Screening	Day 1 (Infusion #1)	Post-Infusion #1 Safety Monitoring	Week 4	Month 3 (Infusion #2)	Post-Infusion #2 Safety Monitoring	Month 4	Month 6 / Early Termination 
Trial Day (Visit Window)	≤30 days prior to Day 1		14 days (±3) after Infusion #1	30 days (± 7)	90 days (±14)	14 days (±3) after Infusion #2	120 days (± 7)	180 (±14)
Informed Consent / Assent	х							
Eligibility Assessment	Х	Х						
Prior & Concomitant Meds	х	Х	х		х	х		Х
Medical History	Х							
Medical Status Questionnaire		х			х			х
Adverse Events	Х	Х	Х		Х	х		х
CAP-1002 IV Infusion 		Х			Х			
Post-Infusion Safety Call 4			Х			х		
Vital Signs		Х			Х			Х
Height / Ulna Length 		Х			Х			х
Weight		Х			Х			Х
Physical Examination		Х			Х			х
12-Lead ECG		Х			Х			х
Serum Chemistry 	Х	Х		Х	Х		Х	х
Hematology 		Х		Х	Х		Х	Х
Cardiac Enzymes 		Х			Х			Х
HLA Typing 		Х						

Protocol No. CAP-1002-DMD-03 Amendment 1.0

Procedure / Event 	Screening	Day 1 (Infusion #1)	Post-Infusion #1 Safety Monitoring	Week 4	Month 3 (Infusion #2)	Post-Infusion #2 Safety Monitoring	Month 4	Month 6 / Early Termination 
Trial Day (Visit Window)	≤30 days prior to Day 1		14 days (±3) after Infusion #1	30 days (± 7)	90 days (±14)	14 days (±3) after Infusion #2	120 days (± 7)	180 (±14)
Donor-Specific Antibodies 		х		Х	х		х	Х
PUL 1.2		Х			Х			Х
6-Minute Walk Test 		Х			Х			х
Pulmonary Function Testing 		х			х			Х
Cardiac MRI 	х							Х

 Sites will complete assessments in the following sequence: 1) safety and other trial assessments, excluding blood collection (e.g., vital signs, height, weight, 12-lead electrocardiogram [ECG], etc.), 2) pulmonary function testing (PFT), 4) PUL 1.2, 5) 6MWT, 6) blood collection, 7) cardiac MRI (if applicable), and 8) CAP-1002 Infusion (if applicable). All efforts must be made for the same clinical evaluator to complete assessments for the same subject at the same time of day throughout the trial (preferably in the morning).

 All attempts must be made to perform the trial assessments indicated for the Month 6 visit (i.e., final comprehensive visit) for subjects that decide to early terminate early from the trial after starting at least one CAP-1002 infusion.

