# 10.8. 14-Day Post-Infusion Monitoring

Subjects will complete a safety, follow-up phone call 14 days (±3 days) after each CAP-1002 infusion to document subject-reported AEs and new concomitant medications.

If clinically indicated, an unscheduled in-person visit will be performed at the investigative site with targeted assessments based on presentation of signs and symptoms of the subject.

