# 5.10 Prior and Concomitant Medications

Prescription, over-the-counter, and alternative medication use will be coded to drug class, preferred drug name, and generic/trade drug name using the World Health Organization Drug Global dictionary (WHODrug Global) version September 1, 2017. Medications that were stopped before the start of the IP administration procedure will be considered "pre-treatment." All other medications will be considered "concomitant." Medications that were started or ongoing at the time the IP administration procedure was started will be considered "baseline" (a subset of "concomitant"). All reported medications will be listed.

Frequencies and percentages of subjects reporting or receiving each medication will be summarized by WHODrug Global Anatomic Therapeutic Chemical (ATC) Level 2 and Preferred Term. Pre-treatment and baseline medications will be summarized separately.

At each level of subject summarization, subjects who reported one or more medications within that level are only counted once for that level.

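### SAP 4.3 drops from the concomitant-medication table any drug begun after the last infusion without a stop date, although SAP 5.10 defines that drug as concomitant

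*SAP*

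**What the plan says.** SAP 4.3 (Handling of Dropouts or Missing Data) presumes that a medication with a missing stop date was in use during the study and has it "counted in the summary table of concomitant medications unless the start date is after the last IP administration".

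SAP 5.10 (Prior and Concomitant Medications) defines the classes. "Medications that were stopped before the start of the IP administration procedure will be considered" pre-treatment, and then "All other medications will be considered" concomitant. Baseline medications are a subset of the concomitant ones. The section plans frequencies and percentages by ATC Level 2 and Preferred Term, in which "subjects who reported one or more medications within that level are only counted once for that level". It adds that "Pre-treatment and baseline medications will be summarized separately" and that "All reported medications will be listed".

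On collection, protocol 10.8 schedules a call 14 days "after each CAP-1002 infusion to document subject-reported AEs and new concomitant medications". Protocol 12.3 captures medications through trial completion. Protocol Table 3 has a row "Prior & Concomitant Meds" that is marked at visits both before and after the second infusion.

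**The concern.** The two SAP sections give different answers for the same drug. Under 5.10 the only date that matters is whether the drug ended before IP administration. A drug that began after the last infusion cannot have done so, so its class is settled without a stop date. Under 4.3 the absence of that date removes it from the table.

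The outcome is also perverse. A drug whose end is unknown, and which may have run longer, is dropped, while the same drug with a known end is kept. This sits badly with the general principle in 4.3 of taking the most conservative date when dates are missing, where concomitant medications are one of the examples given.

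What is at stake is the accuracy of one descriptive table covering the period after the second infusion.

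**Working it through.** The SAP states no figure on this point, so the check compares the rules case by case and then sizes the effect.

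**Inputs**
- Infusions: Day 1 and Month 3, nominal Day 90 ± 14 (protocol Table 3).
- End of follow-up: Month 6, nominal Day 180 ± 14 (protocol Table 3).
- Maximum enrolment: 10 (protocol 7.3).
- Percentages use the subjects in the analysis set with available data (SAP 4).

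**Classification of a drug started on Day 100, after infusion 2 at nominal Day 90**

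| Stop date | Class under SAP 5.10 | Effect of SAP 4.3 | In the table? |
|---|---|---|---|
| Day 110 | Concomitant | Rule not triggered | Yes |
| Missing | Concomitant | Start is after the last infusion, so the exception applies | No |

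The second case arises, for example, when the drug is reported at the call after infusion 2, nominally Day 90 + 14 = 104. Its use on study is then certain, because its start date lies within follow-up.

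**Whether such drugs are meant to be collected.** Table 3 marks medication review at Screening, Day 1, the call after infusion 1, Month 3, the call after infusion 2, and Month 6: six in all. Protocol 10.6 places assessments before the infusion, so the Month 3 review precedes infusion 2. That leaves 2 of 6 reviews after it. This shows intent to collect; it is not an estimate of how often such drugs occur.

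**Period in which the exception can apply**
- Two infusions, nominal: 180 − 90 = 90 days.
- Shortest within the visit windows: (180 − 14) − (90 + 14) = 166 − 104 = 62 days.
- Longest within the visit windows: (180 + 14) − (90 − 14) = 194 − 76 = 118 days.
- One infusion only: the last administration is Day 1, so the exception covers all later follow-up.

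**Effect on a table row.** Each subject is counted once per level. An affected subject who already has another counted drug in the row changes nothing. Otherwise the row loses one subject, or 100/n percentage points: 100/10 = 10.0 at n = 10, and more if fewer are enrolled.

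**Other outputs.** A drug begun after the last infusion is neither pre-treatment nor baseline, so those two summaries are unaffected. The listing of all medications is also unchanged.

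**The case against.** The strongest defence is a softer reading of the sentence. The *unless* may only switch off the presumption of concurrent use, leaving 5.10 to classify late-starting drugs directly. That is grammatically possible. But the clause attaches to being counted in the table, and a programmer following the text would exclude the drug. If both readings are open, the sentence still needs repair.

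A second argument is that the table is barely planned: only 4.3 names it, 5.10 singles out pre-treatment and baseline for separate summary, and protocol 14.4.2 makes study-level summaries optional. The optional wording is the protocol's. The SAP names the table in 4.3, and 5.10 commits to summarizing each medication.

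Third, the clause could be a deliberate restriction to drugs overlapping the dosing period. Neither document says so, and the clause would not achieve it, because late-starting drugs with recorded stop dates stay in.

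Some of the case against stands. Protocol 12.3 asks for stop dates where applicable, so a drug still in use might not be regarded as having a missing one, and the affected set could be small or empty. Protocol 12.3 also speaks of review at each trial visit. If that adds Week 4 and Month 4, the count becomes 3 of 8 rather than 2 of 6, which does not weaken the point. Finally, the 10.0 points is simply one subject in ten; it gives the size of one miscount and says nothing about how many occur.

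**Conclusion.** The point holds. SAP 4.3 as written conflicts with the definition in SAP 5.10 and leaves out of the concomitant-medication table drugs that belong there. Severity is low. The understatement per affected subject and row is 0 or 1/n, at least 10.0 percentage points in the latter case because n is at most 10. It is confined to one descriptive table, and no endpoint or analysis population is touched.

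The conclusion rests on the literal reading of the 4.3 sentence. The total size depends on how many drugs begun after the last infusion lack a stop date, and on whether ongoing drugs are treated as lacking one. The documents settle neither. If ongoing drugs are so treated, every drug begun after infusion 2 and still in use at Month 6 is omitted.

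**What to change.** In SAP 4.3, delete the clause beginning with *unless*, so that any medication with a missing stop date is counted as concomitant, in agreement with SAP 5.10. The question of ongoing versus missing stop dates then no longer matters for late-starting drugs in this table, since they are counted either way.

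The cost is one clause in the SAP. No new data are needed and the listings stay as they are. The deletion should not bring in drugs taken after the study, because protocol 12.3 already ends capture at trial completion.
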